APPENDIX 2. ADVERSE EVENTS OF SPECIAL INTEREST PREFERRED TERMS

- Anemia;
- Diarrhea;
- Fatigue;
- Blood FSH decreased;
- Blood FSH increased;
- Weight decreased;
- Weight increased;
- Decreased appetite;
- Hypersomnia;
- Lethargy;
- Sedation;
- Seizure;
- Somnolence;
- Status epilepticus;
- Aggression;
- Agitation;
- Irritability;
- Acute respiratory failure;
- Dyspnea;
- Respiratory arrest.

APPENDIX 3. LABORATORY TESTS

Analytical Testing

Hematology	white blood cells, red blood cells, platelet count, neutrophils, lymphocytes, eosinophils, basophils, monocytes, hemoglobin, and hematocrit
Serum Chemistry	total protein, albumin, creatinine, Blood urine nitrogen (BUN), uric acid, total bilirubin, direct bilirubin, alkaline phosphatase, FSH, AST, ALT, glucose, calcium, phosphorus, bicarbonate, chloride, sodium, and potassium
Urinalysis	specific gravity, pH, color, and presence of white blood cells (WBCs), red blood cells (RBCs), and proteins
Pregnancy test	β human chorionic gonadotropin (β -hCG) in urine

Document: C:\Users\q832483\Documents\Insy CSR\Pending\Ready for QC\New folder\Statistical Analysis Plan.docx
Author: [REDACTED] Version Number: V1.0 Final
Version Date: 04APR2017

Template No: CS_TP_BS016 – Revision 3
Effective Date: 01May2012

Reference: CS_WI_BS005

[figure not shown]

Document: C:\Users\q832483\Documents\Insy CSR\Pending\Ready for QC\New folder\Statistical Analysis Plan.docx
Author: [REDACTED] Version Number: V1.0 Final
Version Date: 04APR2017

Template No: CS_TP_BS016 – Revision 3
Effective Date: 01May2012

Reference: CS_WI_BS005

PHARMACOKINETIC STATISTICAL ANALYSIS PLAN

Insys Development Company
Clinical Trial Protocol INS011-14-030
A multicenter, open-label, flexible dose study to assess the long-term safety of pharmaceutical Cannabidiol Oral Solution as an adjunctive treatment for pediatric and adult subjects with a treatment-resistant seizure disorder who complete INS011-14-029 or Part A of INS011-15-054

Pharmacokinetic Statistical Analysis Plan
11 July 2017

[REDACTED]

Page 2 of 12

Pharmacokinetic Statistical Analysis Plan
Insy Clinical Trial Protocol INS011-14-030

SIGNATURES

Statistician:
Title

[REDACTED]
Ph.D.

Signature/Date:

[REDACTED]
11 July 2017

Pharmacokineticist:
Title

[REDACTED]
Ph.D.

Signature/Date:

[REDACTED]
11 Jul 2017

Pharmacokineticist:
Title

[REDACTED]
Ph.D.

Signature/Date:

[REDACTED]
11 Jul 2017

Sponsor Approval:
Title

[REDACTED]
Ph.D.

Insy Development Company

Signature/Date:

[REDACTED]
11 Jul 2017

[REDACTED]
Page 3 of 12Pharmacokinetic Statistical Analysis Plan
Insys Clinical Trial Protocol INS011-14-030**LIST OF COMMON ABBREVIATIONS AND DEFINITIONS OF TERMS**

ANOVA	analysis of variance
AUC	area under the (plasma concentration vs. time) curve
bid or BID	twice daily
BLQ	below the limit of quantitation
CI	confidence interval
CL/F	clearance after extravascular administration
C _{max}	maximum concentration
CV%	percent coefficient of variation
h	hour(s)
ln	natural logarithm
mg	milligram(s)
mL	milliliter(s)
n or N	number of occurrences
N/A or NA	not applicable
ng	nanogram(s)
PK	pharmacokinetic(s)
qd or QD	once daily
SAP	statistical analysis plan
SD	standard deviation
t _{1/2}	terminal elimination half-life
T _{max}	time to reach C _{max}
[REDACTED]	
Vz/F	Volume of distribution in the terminal phase after extravascular administration
λ _z	apparent elimination rate constant in terminal phase

Pharmacokinetic Statistical Analysis Plan
Insy Clinical Trial Protocol INS011-14-030

STUDY TITLE

A multicenter, open-label, flexible dose study to assess the long-term safety of pharmaceutical Cannabidiol Oral Solution as an adjunctive treatment for pediatric and adult subjects with a treatment-resistant seizure disorder who complete INS011-14-029 or Part A of INS011-15-054

STUDY OBJECTIVES

The primary objectives of this study are:

- To assess the long-term safety of Cannabidiol Oral Solution as an adjunctive treatment for subjects with treatment-resistant seizure disorders, including Lennox-Gastaut syndrome (LGS) or Dravet syndrome (DS)
- To establish the continued efficacy of Cannabidiol Oral Solution in maintaining seizure control in subjects with treatment-resistant seizures that previously completed INS011-14-029, INS011-14-024, or INS011-14-025
- To assess the global status of subjects taking Cannabidiol Oral Solution for an extended period of time determined by various qualitative assessments
- To monitor for changes in plasma levels of Cannabidiol Oral Solution during long-term treatment of subjects with treatment-resistant seizure disorders, including LGS or DS

STUDY DESIGN

This is a multicenter, open-label study to assess the long-term safety and efficacy of Cannabidiol Oral Solution as adjunctive therapy for pediatric and adult subjects with treatment-resistant seizure disorders, including LGS and DS.

In this study, all subjects will be dosed as follows:

- Subjects who completed INS011-14-029 will initiate this study on the dose with which they were being treated previously, unless tolerability issues were observed for a particular subject. When the dose is selected for INS011-14-024 and INS011-14-025, subjects will be transitioned to that dose (a maximum of 40 mg/kg/day).
- Subjects who completed INS011-14-024 and INS011-14-025 will continue treatment with the dose at which they were being treated previously, unless tolerability issues were observed for a particular subject. This dose will be that deemed safe and tolerable in INS011-014-029.

The planned dosing regimen is twice daily administration (BID).

[REDACTED]

Page 5 of 12

Pharmacokinetic Statistical Analysis Plan
Insy Clinical Trial Protocol INS011-14-030

Dosing of the investigational product may be reduced for an individual subject as per Investigator opinion should tolerability issues arise. Treatment with established antiepileptic drugs (AEDs) will continue without interruption and changes will be permitted as necessary based on safety concerns of changes in seizure control.

Visits will be scheduled at 1 week, 2 weeks, and monthly for the first 3 months after completion of the subject's prior study, and quarterly thereafter. All subjects will complete a Final Visit/Discontinuation Visit regardless of when they stop treatment/complete the study. A Follow-up Visit will occur 2 weeks after the Final Visit/Discontinuation Visit.

At each visit, a record of the incidence and severity of AEs, treatment-emergent AEs (TEAEs), and SAEs will be collected and this will serve as a primary outcome criterion for this study. Other safety-related parameters such as 12-lead ECG and hematology, chemistry, and urinary analyses will also be assessed at each visit except the 2-week visit.

At each visit except the 1- and 2-week visits, the following qualitative assessments will be completed: Clinical Global Impression of Improvement (CGI-I), Clinical Global Impression of Severity (CGI-S), Child Behavior Checklist (CBCL) Total Problems scale, Impact of Pediatric Epilepsy Scale (IPES), Vineland Adaptive Behavior Scales (VABS), Vineland Maladaptive Behavior Scales (VMBS), and Columbia-Suicide Severity Rating Scale (C-SSRS).

Seizure diaries will be reviewed to assess control of seizures (frequency, duration, and severity) throughout the duration of the study.

Collection of Pharmacokinetic Samples

Determination of trough (pre-dose) plasma levels of cannabidiol (CBD) and its 7-OH metabolite (7-OH-CBD) will be performed. Samples for assessment of CBD and 7-OH CBD trough plasma levels will be collected immediately prior to administration of the morning dose of the investigational product at the following times:

- Visit 2 (Day 1, Week 0)
- Visit 5 (Week 4)
- Visit 6 (Week 8)
- Visit 7 (Week 12)
- Visit 8 (Week 24)
- Visit 9 (Week 36)
- Visit 10 (Week 48, TBD; final visit)*
- Visit 11 (Week 50, TBD; 2 weeks after final visit)*

*Subjects continuing on study medication as part of the Expanded Access Program will be flagged in the concentration-time listings; the concentration-time data for this subset of the population will be summarized in a secondary set of tables and figures.

[REDACTED]

Page 6 of 12

Pharmacokinetic Statistical Analysis Plan
Insy Clinical Trial Protocol INS011-14-030

For patients taking clobazam, plasma levels of clobazam and its major metabolite norclobazam will also be measured.

The following information will be captured for blood sample collection in each subject's eCRF:

- Subject number and initials
- Visit
- Time and date of most recent administration of the investigational product prior to the sample collected for plasma level analysis
- Dose of most recent administration of the investigational product prior to the sample collected for plasma level analysis
- Time and date of each blood sample collected for plasma level analysis
- Dose, formulation, and dosing regimen of clobazam, if applicable, prior to the PK collection
- Time and date of subject's ingestion of food (i.e., the evening meal on the day prior to each study visit).

PHARMACOKINETIC METHODS

Concentration-time data will be analyzed using Phoenix™ WinNonlin® (Version 6.3 or higher, Pharsight Corporation) or other appropriate software. These data will support safety monitoring and establish the extent of variability during long-term treatment with the investigational product.

Pharmacokinetic Population

The PK population consists of patients who receive at least one dose of CBD and have at least one usable CBD plasma concentration measurement.

Concentration-Time Data Tabulation

Concentration data of CBD, 7-OH-CBD, clobazam, and norclobazam (N-desmethylclobazam), if applicable, will be presented in a data listing. The listing will include Subject ID, Subject Alias, Visit (or Week), Actual Time Post Dose (if available), CBD Dose, Clobazam Dose, formulation, and dosing frequency (if applicable), and concentration (units) for each analyte.

Concentration data of CBD and 7-OH-CBD will be tabulated and summarized by CBD dose level (based on the daily dosing regimen, mg/kg/day, of CBD when the plasma sample is taken) at each collection time (scheduled week) using descriptive statistics (n, mean, SD, minimum, median, maximum, and percent coefficient of variation). In addition, dose-normalized concentrations of CBD and 7-OH-CBD will be tabulated and summarized by clobazam flag

Pharmacokinetic Statistical Analysis Plan
Insy Clinical Trial Protocol INS011-14-030

(yes/no) at each collection time (scheduled week) using descriptive statistics. CBD and 7-OH-CBD concentration-time data for subjects continuing on study medication as part of the Expanded Access Program will be summarized in a secondary set of tables and figures.

Concentration data of clobazam and norclobazam will be stratified by clobazam flag (yes/no), tabulated, and summarized using descriptive statistics.

In the data tabulation and summarization, concentrations below the lower limit of quantitation (BLQ) will be set to zero.

Plots of mean concentration-time for CBD and 7-OH-CBD and dose-normalized CBD and 7-OH-CBD will be created by CBD dose level, with and without stratification by clobazam (yes/no). Plots of concentration-time data for CBD and 7-OH-CBD for individual subjects will be created; since the dose level may vary during the study, the dose level at a given sample time will be labeled or foot-noted (if possible) in the figure. Plots for clobazam and norclobazam will be stratified by subjects on clobazam therapy (yes/no).

Pharmacokinetic Calculations

The metabolite-to-parent ratio (MRCtrough) will be calculated using concentrations of 7-OH CBD (metabolite) and CBD (parent) at each Visit, starting with the first trough sample obtained and through the remaining visits. If either CBD or 7-OH CBD concentration is not reportable or BLQ, MRCtrough will be reported as "not applicable". MRCtrough for clobazam will be calculated using the same methodology.

To assess the degree of accumulation during long-term BID administration of cannabidiol oral solution after 1 month treatment (Visit 5), an accumulation ratio (RCtrough) will be estimated using the dose-normalized trough plasma concentrations of CBD and 7-OH-CBD at each Visit, according to:

$$RCtrough = \text{Conc}/D(n^{\text{th}} \text{ visit dose})/\text{Conc}/D(5^{\text{th}} \text{ visit dose}),$$

where $\text{Conc}/D(n^{\text{th}} \text{ visit dose})$ is the dose-normalized trough concentration at a given Visit beyond 1 month (i.e., n^{th}) and $\text{Conc}/D(5^{\text{th}} \text{ visit dose})$ is the dose-normalized trough concentration determined at Visit 5 (scheduled on Week 4). If either $\text{Conc}/D(n^{\text{th}} \text{ visit dose})$ or $\text{Conc}/D(5^{\text{th}} \text{ visit dose})$ is not reportable or BLQ, RCtrough will be reported as "not applicable".

RCtrough and MRCtrough will be tabulated and summarized by CBD dose level (based on the daily dosing regimen, mg/kg/day, of CBD when the plasma sample is taken) at each collection time (week) using descriptive statistics (n, mean, SD, minimum, median, maximum, and percent coefficient of variation). MRCtrough for clobazam will be stratified by clobazam flag (yes/no), tabulated, and summarized using descriptive statistics.

[REDACTED]

Page 8 of 12

Pharmacokinetic Statistical Analysis Plan
Insy Clinical Trial Protocol INS011-14-030

REPORTING

The pharmacokinetic tables and figures described in this PK SAP will be presented in the listings section of the clinical study report (CSR) for INS011-14-030. Appropriate numbering to be provided by the medical writer.

GENERAL REFERENCES

- “Guidance For Industry: Statistical Approaches to Establishing Bioequivalence” U.S. Department of Health and Human Services Food and Drug Administration Center for Drug Evaluation and Research (CDER) January 2001.
- “Guidance For Industry: Bioavailability and Bioequivalence Studies for Orally Administered Drug Products-General Considerations” U.S. Department of Health and Human Services Food and Drug Administration Center for Drug Evaluation and Research (CDER) March 2003.
- “Guidance For Industry: Food-Effect Bioavailability and Fed Bioequivalence Studies” U.S. Department of Health and Human Services Food and Drug Administration Center for Drug Evaluation and Research (CDER) December 2002.
- “Guidance For Industry: Drug Interaction Studies – Study Design, Data Analysis, Implications for Dosing, and Labeling Recommendations” U.S. Department of Health and Human Services Food and Drug Administration Center for Drug Evaluation and Research (CDER) February 2012.
- Brian P. Smith, Francois R. Vandenbende, Karl A. DeSante, Nagy A. Farid, Pamela A. Welch, John T. Callaghan, and S. Thomas Forgue, “Confidence Interval Criteria for Assessment of Dose Proportionality”, *Pharmaceutical Research*, Vol. 17, No. 10, 2000; p.1278-1283.

[REDACTED]

Page 9 of 12

Pharmacokinetic Statistical Analysis Plan
Insy Clinical Trial Protocol INS011-14-030

EXAMPLE TABLES AND FIGURES

Concentration listing with descriptive statistics

Analyte	CBD_Dose (mg/kg)	Subject_ID	Subject_Alias	Visit						
				2	5	6	7	8	9	10
Cannabidiol	5.00	xxx	xxx							
				n						
				Mean						
				SD						
				Min						
				Median						
				Max						
				CV%						

Similar format for each analyte, dose level, and for dose-normalized concentrations

Concentration summary table

Analyte		Visit 2			Visit 5
		Concentration (ng/mL)	DN_Concentration (ng/mL/mg/kg)	CBD_Dose (mg/kg)	
Cannabidiol	n Mean SD Min Median Max CV% Geometric Mean				

[figure not shown]
Similar table for 7-OH CBD

[REDACTED]

Page 10 of 12

Pharmacokinetic Statistical Analysis Plan
Insys Clinical Trial Protocol INS011-14-030

Mean Figures

Similar format for all figures

Page 11 of 12

Pharmacokinetic Statistical Analysis Plan Insys Clinical Trial Protocol INS011-14-030

MRCthrough table

			Visit							
			2	5	6	7	8	9	10	
CBD_Dose (mg/kg)	Subject_ID	Subject_Alias	MRCTrough_CBD							
5.00	xxx	xxx								
			n							
			Mean							
			SD							
			Min							
			Median							
			Max							
			CV%							

RCTrough table

				Visit				
				6	7	8	9	10
Analyte	CBD_Dose (mg/kg)	Subject_ID	Subject_Alias	RCTrough				
Cannabidiol	5.00	xxx	xxx					
				n				
				Mean				
				SD				
				Min				
				Median				
				Max				
				CV%				

[REDACTED]
Page 12 of 12Pharmacokinetic Statistical Analysis Plan
Insys Clinical Trial Protocol INS011-14-030

Concentration listing

Analyte	Subject ID	Subject Alias	Visit	Week	CBD Daily Dose (mg/kg/day)	Prior Visit CBD Dose (mg/kg)	Clobazam Dose (mg)	Route Of Clobazam	Dose Frequency Of Clobazam	Conc (ng/mL)
CBD	xxx	xxx	5	4	20.00	10.00	10.00	ORAL	QD	xxx
CBD	xxx	xxx	6	8	20.00	10.00	10.00	ORAL	QD	xxx
CBD	xxx	xxx	7	12	20.00	10.00	10.00	ORAL	QD	xxx

Note: This listing will be based on the analysis data set provided by the statistician or biostatistics group.

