6.2 Plasma Levels

Whole blood will be obtained in a Vacutainer® containing heparin anticoagulant for the determination of the plasma levels of cannabidiol and 7-OH cannabidiol in human plasma. The sample will be obtained as indicated in Table 1 prior to daily study medication dosing on that day. Samples for plasma level assessment of cannabidiol and 7-OH cannabidiol should

be collected immediately prior to administration of the morning dose of the investigational product on indicated days.

The following information will be captured for blood sample collection in each subject's eCRF:

- Subject number and initials
- Time and date of most recent administration of the investigational product prior to the sample collected for plasma level analysis
- Time and date of each blood sample collected for plasma level analysis
- Time and date of subject's ingestion of food (i.e., the evening meal on the day prior to each study visit).

Samples for the determination of the investigational product in human plasma will be analyzed by the Sponsor, using an appropriate bioanalytical method. It is anticipated that this will include estimates of concentration and trough (steady state) concentration of cannabidiol and 7-OH cannabidiol (monthly to quarterly). For subjects taking clobazam, levels of clobazam and its major metabolite (norclobazam) will be measured if there are safety concerns.

The analytical method for human plasma will be developed and validated. All samples still within the known stability of the investigational product will be analyzed.

Exploratory plasma samples will be shipped to the Sponsor or the Sponsor-designated bioanalytical laboratory.

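### The PK SAP groups clobazam and norclobazam levels only by clobazam use, so these summaries cannot show an effect of cannabidiol on clobazam levels

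*SAP*

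**What the plan says.** The PK SAP is bound behind the main SAP, whose section 16.1 defers all PK analysis to it. Under Concentration-Time Data Tabulation it states: "Concentration data of clobazam and norclobazam will be stratified by clobazam flag (yes/no), tabulated, and summarized using descriptive statistics". Under Pharmacokinetic Calculations it adds: "MRCtrough for clobazam will be stratified by clobazam flag (yes/no), tabulated, and summarized using descriptive statistics". The clobazam and norclobazam plots are split the same way.

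On who contributes samples, the PK SAP (Collection of Pharmacokinetic Samples) says: "For patients taking clobazam, plasma levels of clobazam and its major metabolite norclobazam will also be measured". Protocol 6.2 is narrower: "For subjects taking clobazam, levels of clobazam and its major metabolite (norclobazam) will be measured if there are safety concerns". On low values, the PK SAP says: "In the data tabulation and summarization, concentrations below the lower limit of quantitation (BLQ) will be set to zero". A metabolite ratio is reported as not applicable when either component is unreportable or below quantitation.

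The clobazam dose is available. The PK SAP's list of information to be captured with each blood sample includes: "Dose, formulation, and dosing regimen of clobazam, if applicable, prior to the PK collection". For cannabidiol itself the plan is fuller. Levels are summarised by cannabidiol daily dose at sampling and by scheduled week, and in addition "dose-normalized concentrations of CBD and 7-OH-CBD will be tabulated and summarized by clobazam flag" at each collection time.

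**The concern.** Clobazam use is a sensible grouping for cannabidiol levels. Applied to clobazam's own levels, it separates people who take a drug from people who do not. Neither cannabidiol dose nor cannabidiol exposure enters the grouping, and the levels are not normalised for clobazam dose.

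The protocol gives a reason to care about this direction. Section 1.4 lists possible CYP3A4 and CYP2C19 inhibition among the potential concerns. Section 6.1.1.1 asks sites to watch for adverse events from altered metabolism of background antiepileptics. Clobazam and norclobazam are the only background-drug analytes named for plasma measurement, and main SAP 17.1.6 plans to relate somnolence to clobazam administration. The PK SAP tables are the only planned summary of clobazam concentrations. If they cannot respond to cannabidiol, those assays reach the report only as a listing.

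**Working it through.** The documents give no sample size, power or target effect for this point, so there is no figure to reproduce. The check sets the planned groupings side by side and then adds illustrative arithmetic.

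**1. Groupings named in the PK SAP text**

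| Quantity | Grouping | Normalised for dose |
|---|---|---|
| Cannabidiol, 7-OH-cannabidiol | Cannabidiol daily dose at sampling, by week; dose-normalised levels also by clobazam flag | Yes, cannabidiol dose |
| Cannabidiol metabolite ratio | Cannabidiol daily dose at sampling, by week | Not applicable |
| Clobazam, norclobazam | Clobazam flag only | No |
| Clobazam metabolite ratio | Clobazam flag only | Not applicable |

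**2. Content of the clobazam contrast.** Non-users are not due to be assayed. If one is, the value will usually be below quantitation and enter as 0, and the metabolite ratio will be not applicable. The user mean may rise if cannabidiol raises norclobazam, but no column by cannabidiol dose or off cannabidiol stands beside it. Visit 2 does not supply one for subjects who roll over without interruption, because they enter already on cannabidiol.

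**3. Raw means among users (assumed values).** Let *k* be the fold change in norclobazam per mg of clobazam and *f* the fraction of users whose clobazam is halved, which Protocol 4.3 allows. With levels proportional to clobazam dose:

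observed ratio of raw means = *k* × (1 − *f* + 0.5*f*)

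- *k* = 2, *f* = 0.5: 2 × 0.75 = 1.5
- *k* = 2, *f* = 1: 2 × 0.5 = 1.0
- *k* = 1, *f* = 0.5: 1 × 0.75 = 0.75, a 25% fall with no interaction

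Divided by clobazam dose, the ratio is *k* in each case. This applies to raw concentrations only. In norclobazam/clobazam the halving cancels: with clobazam per mg unchanged, (2 × 0.5)/(1 × 0.5) = 2. The ratio's weakness is the missing comparator.

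**4. What regrouping would yield.** Assumptions, not from the documents: all 80 subjects (60 + 20) enrol, 25% or 50% take clobazam, users split equally over 10, 20 and 40 mg/kg/day, levels are lognormal with CV 80%, and the effect is linear in cannabidiol dose with multiplier *m* at 40. The expected 40-versus-10 ratio is *m* / (1 + (*m* − 1)/4): 1.0 for *m* = 1, 2/1.25 = 1.6 for *m* = 2, and 3/1.5 = 2.0 for *m* = 3. Simulation (4,000 runs) gave medians of about these values, with these 5–95% ranges:

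| *m* | 6 per dose | 13 per dose |
|---|---|---|
| 1 | 0.48–2.05 | 0.61–1.67 |
| 2 | 0.79–3.33 | 0.98–2.68 |
| 3 | 0.97–4.10 | 1.22–3.27 |

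The regrouped table moves with the effect, but loosely.

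**The case against.** A reader might infer that the plan cannot show any cannabidiol–clobazam interaction. The documents do not support that. Dose-normalised cannabidiol and 7-OH-cannabidiol by clobazam flag address the effect of clobazam on cannabidiol. Under the same assumptions with half of subjects on clobazam, a true doubling gives a median yes/no ratio of 2.00 (5–95%: 1.48–2.65). Only the effect of cannabidiol on clobazam is missing.

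The strongest textual counter is the first example shell. It has cannabidiol-dose rows and visit columns, and a note extends its format to each analyte. That could be read as a clobazam table by cannabidiol dose, so the shells and text need aligning. But the text gives the clobazam analytes their own sentences with the flag alone. The concentration summary shell is extended only to 7-OH-cannabidiol, its normalisation is per mg/kg of cannabidiol, and the metabolite-ratio shell is for cannabidiol.

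Other points stand in part. The listing puts cannabidiol dose, clobazam dose and concentration together, but it is not a summary. The stated objectives cover cannabidiol levels (and 7-OH in Protocol 2.1), not clobazam, and Protocol 6.1.1.1 leaves decisions about background drugs to case-by-case judgement. That limits the importance. The flag's timing is undefined, so someone who recently stopped clobazam and is flagged as a non-user could have measurable levels. The contrast is therefore almost, not strictly, settled in advance. Nobody is likely to mistake a user/non-user difference for an interaction. The cost is an uninformative table, not a false finding.

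**Conclusion.** The point holds for one direction. As worded, the planned summaries and plots of clobazam, norclobazam and their ratio cannot show an effect of cannabidiol on clobazam levels, because their only grouping is clobazam use and assays are planned in users. This follows from the text and needs no assumed values. The dilution of raw means (1.5 or 1.0 for a true doubling) rests on assumed dose changes and does not extend to the metabolite ratio.

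A second problem sits underneath. If assays are done only where there are safety concerns, as Protocol 6.2 says, the clobazam group is selected on suspected problems. If all users are assayed, as the PK SAP says, it is not. The two passages must be reconciled before any clobazam summary can be interpreted.

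The point is worth correcting, but it affects neither the primary safety outcome nor any stated objective.

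**What to change.** In the PK SAP:

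- Restrict the clobazam, norclobazam and clobazam metabolite-ratio tables and plots to samples taken on clobazam. Define the flag per sample and drop the yes/no split for these analytes.
- Summarise clobazam and norclobazam raw and divided by clobazam daily dose at sampling.
- Group these and the ratio by cannabidiol daily dose at sampling and by visit, with off-cannabidiol samples as a separate level.
- Align the example shells, stating which analytes each covers and which dose is used for normalisation.
- Reconcile the PK SAP with Protocol 6.2 on who is assayed, and report how many clobazam users have samples at each visit.

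Optionally, add a descriptive within-subject comparison of the last on-cannabidiol sample with Visit 11 in clobazam users who stopped cannabidiol. It needs caveats. Visit 11 falls 9 to 19 days after the final visit (14 ± 5). Under Protocol 4.1.2 a taper should be complete before Visit 10, so the last on-drug sample may be from Week 36, about 14 weeks before Week 50. Antiepileptics may change in between, and the documents give no norclobazam half-life.

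The cost is PK SAP wording and shells, plus a protocol clarification if the sampling rule changes. The dose and concentration inputs are already in the planned listing. The downside is sparse strata and a comparison by cannabidiol dose that is not randomised, since dose follows efficacy and tolerability (Protocol 4.1.1). The results remain descriptive.
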